For all participants who are age 60 years or older, an EKG will be completed at baseline, or at the next visit time point for all active study participants. EKGs will be completed at baseline for 2 patients currently pending their baseline visits. For all currently active patients who have already completed their baseline visit, an EKG will be completed at their next in-person visit (Week 12 or 26 or 52). EKGs will only be repeated at the subsequent study visits if an abnormality is present during the patient's initial EKG. All EKG abnormalities will be reviewed with the patient's primary care physician (all patients have an outside primary care physician). The patient's primary care physician and the study team will work together to determine whether any action is indicated and if it is safe for the patient to continue in the protocol. While the study medication Valacyclovir does not have any listed cardiac side effects neither in its medlineplus.gov web page <https://medlineplus.gov/druginfo/meds/a695010.html> nor in its package insert https://www.accessdata.fda.gov/drugsatfda_docs/label/2005/020487s007rel2_lbl.pdf, acyclovir, which is what Valacyclovir is converted into after first pass metabolism, does have Tachycardia listed as a rare side effect in its medlineplus.gov information page <https://medlineplus.gov/druginfo/meds/a681045.html>. While we obtain heart rate at each in-person study visit, we will obtain this reading, more precisely, from the EKG and act on it as follows: any patient with a measure of heart rate over 100 beats per minute will be asked to suspend their administration of study medication in the study and await clearance by their primary care physician for re-entry into the study.

Computer and Database Facilities - Data Coordination:

The data collected in this study will be entered and monitored by the Database Management Unit at NYSPI. This unit is headed by [name], whose unit has 2000 square feet of office space, and can easily accommodate the data management activities in this proposal.

The unit will work closely with the research assistant/coordinator and the Principal Investigator to facilitate independent auditing of primary subject records. The database will provide reports indicating all modifications that have been made in the database together with paper communications (fax, e-mail) confirming and authorizing these modifications.

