As indicated in preceding section, structural baseline MRI will be completed at NYSPI MRI Suite, or at CU's MBBI facility. If the subject had positive, veritable medical records indicating AD biomarker positivity (via historic Amyloid PET or CSF) for confirmation of inclusion/exclusion criteria, the patient will complete an 18F- Florbetapir PET scan at Baseline.

At this time patients will receive 2-4g of valacyclovir. The oral valacyclovir will be distributed in 500mg pills, so patients will take 4-8 pills per day. Participants are randomized to receive either valacyclovir or placebo. Valacyclovir is titrated from 2g to 4g daily over 4 weeks, with initiation of 2g daily dosing at Baseline. Dosing is monitored by the Study Physician. The maintenance dose of valacyclovir is 4g daily per protocol, for the rest of the 52 week trial. If the participant cannot tolerate the dose of 4 g daily, they can continue to receive active medication treatment as long as they receive at least 2 g daily. Patients will be asked to return the pill bottles with any remaining pills at following visits. The research assistant will record the number of returned pills to confirm adherence to medication procedure.

2-WEEK VISIT (Telephone Call)

The telephone call at 2 weeks is primarily a clinical call to monitor the patient's status on valacyclovir/placebo 2 g/day and raise it to 3 g daily (at 2 weeks).

The patient will be clinically assessed by the Study Physician by telephone.

Adverse events will be collected and documented by the Research Assistant, for review and follow up between the patient and Study MD. The study physician will document the study visit in a typed progress note.

4-WEEK VISIT (Telephone Call)

The telephone call at 4 weeks is primarily a clinical call to monitor the patient's status on valacyclovir/placebo 3 g/day and raise it to 4 g daily. Targeted dose is 4 g daily.

The patient will be clinically assessed by the Study Physician by telephone.

Adverse events will be collected and documented by the Research Assistant, for review and follow up between the patient and Study MD. The study physician will document the study visit in a typed progress note.

12-WEEK VISIT

The patient will be clinically assessed by the Study Physician (symptom driven physical exam will be performed and vital signs collected).

An EKG will be completed for all participants who are age 60 or older, if they did not receive one at their baseline visit.

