Neuropsychological testing and rating scales: the PACC; ADCS-ADL-PI; UPSIT and the CIBIC-Plus- Clinician's Interview-Based Impression of Change will be completed.

Adverse events will be collected and documented by the Research Assistant, for review and follow up between the patient and Study MD. The study physician will document the study visit in a typed progress note.

Blood will be drawn for the following laboratory analyses: SMAC blood chemistry; Complete Blood Count, as well as blood drawn for later analysis of plasma acyclovir levels. Patient will need to return all unused pills.

26-WEEK VISIT

The patient will be clinically assessed by the Study Physician (symptom driven physical exam will be performed and vital signs collected). The study physician will document the study visit in a typed progress note.

An EKG will be completed for all participants who are age 60 or older, if they did not receive one at their baseline visit.

Neuropsychological testing and rating scales: the PACC; CDR (sum of boxes); ADCS-ADL-PI; NACC Physician Evaluation; UPSA and the CIBIC-Plus-Clinician's Interview-Based Impression of Change will be completed.

Blood will be drawn for the following laboratory analyses: SMAC Blood Chemistry and Complete Blood Count.

Adverse events will be collected and documented by the Research Assistant, for review and follow up between the patient and Study MD. The study physician will document the study visit in a typed progress note.

Blood will be drawn for the following laboratory analyses: SMAC blood chemistry; Complete Blood Count, as well as blood drawn for later analysis of plasma acyclovir levels. Patient will need to return all unused pills.

52-WEEK VISIT (End Point or Drop Out Visit)

The patient will be clinically assessed by the Study Physician (complete physical exam will be performed and vital signs collected). Re-evaluation of diagnosis will be completed. The study physician will document the study visit in a typed progress note.

Adverse events will be collected and documented by the Research Assistant, for review and follow up between the patient and Study MD.

Neuropsychological testing: the PACC; UPSIT, CDR (sum of boxes); ADCS-ADL- PI; UPSA; NACC Physician Evaluation and the CIBIC-Plus-Clinician's Interview-Based Impression of Change will be completed.

Physical Activity Assessment Scale will be completed.

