Define criteria that will be used to exit or drop subjects from the study and operationalize. Indicate the time points when such criteria will be applied, and describe the rating instruments, parameters, and thresholds that will lead to a decision to terminate a subject's participation and the role of the person who will make these determinations. Studies which include a medication taper and discontinuation may be asked to include an independent medical monitor (an MD not on the study team) who will aid the study team in determining whether study discontinuation is needed. In addition, explain procedures for managing subjects who are withdrawn from the protocol.

Protocol Summary Form

For treatment studies: To minimize risks to subjects, operationalized drop-out criteria should be defined so that subjects who worsen, or in some cases, fail to improve, are removed from the study and offered standard care. The threshold for drop-out should consider the level of risk associated with non-improvement for the specific disorder, the availability of alternatives, and the typical required duration of treatment. For example, emergence of suicidal intent, or psychosis, should prompt immediate clinical evaluation and withdrawal from the study.

The reasons for early discontinuation of a patient from the study are as follows:

- 1.) Intervening severe medical illness that the PI determines to be grounds for study discontinuation. Medical monitoring is done by the study staff (PI and study physicians; research coordinators gather information and convey any such information to the study physician and PI). All medically relevant decisions are made only by study physicians and the PI. The DSMB monitors the progress of the study including medical issues; all SAEs are reported immediately to the DSMB.
- 2.) Discontinuation of treatment with valacyclovir or placebo for more than 6 weeks. After an interruption of treatment for any reason, e.g., medical illness, the patient can resume the protocol if the interruption is less than 6 weeks.

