- 3.) Based on the result of a blood draw at the week 12 visit, if the serum creatinine level increases to be greater than 1.5 mg/dl, or eGFR declines to less than 44 mL/min, we will lower the study medication to the minimum dose of 2 g valacyclovir or placebo per day. Patients will then have blood collected and labs repeated at an additional visit, at week 16. If, at week 16, kidney function is still abnormal based on the above criteria, study medication will be discontinued for this patient. The reduction in kidney function will be communicated to the patient's primary care physician.
- 4.) The patient will be discontinued if 1) the CIBIC-PLUS score is higher than 80 (consistent with moderate dementia or moderate to severe behavioral changes), or if 2) the C-SSRS score is 6 or higher on the Suicidal Ideation Subscale, or if there is any positive score on the Suicidal Behavior Subscale or Behavior Lethality Subscale.

If MRI Acquisition must be terminated for some reason, the patient can still continue in the protocol. This is because MRI outcomes are secondary and not primary.

This is an intent-to treat protocol. Therefore, a patient who is discontinued early in the study due to the above reasons will be followed and evaluated (whenever feasible) until the Week 52 visit, or until the patient withdraws his/her consent to participate.

Blood and other Biological Samples

Describe how the sample will be used and indicate, when relevant, the amount of the sample. The IRB wants to know that the sample is sufficient for the purposes of the study, but that sampling is limited to what is minimally necessary.

If you've indicated that you intend to store a sample for future use, indicate where the sample will be stored, how long the sample will be stored, and to what purposes the sample will eventually be put. Check the IRB website at <https://irb.nyspi.org/investigators/guidance/genetic-research> for specific guidance and additional information about future use of DNA samples.

Protocol Summary Form

Routine Laboratory Tests: At Screening, Weeks 12, 26 and 52, blood will be collected for the following screening laboratory tests, which will be performed by the OMH Clinical Laboratories-Nathan Kline Institute: CBC, BUN, creatinine, eGFR, electrolytes, liver and thyroid function studies, B-12, and folate (a total of 20 mL blood will be collected across all four timepoints).

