Informed Consent: Informed consent is obtained and documented with a signed consent statement giving full information about the study. In the consent form and in discussion with an investigator, subjects are advised fully of the procedures to be used, the amount of time required of them, the fact that this is a longitudinal treatment study with repeated assessment at specified time points, the possible risks and benefits of the procedures and the treatment conditions, their right to refuse participation in the study without prejudice, their right to terminate participation at any moment without prejudice, and the name and telephone number of the Principal Investigator. All informants will be required to sign the "Informant Information Sheet" to indicate that they agree to the responsibilities detailed in the document.

Capacity to Consent: Based on IRB requirements, patients will be recruited by a study physician who signs the consent form in addition to the patient. As described earlier, for patients who lack the capacity to consent but retain the capacity to appoint a surrogate, we will follow the procedures required by the NYSPI IRB (based on New York State OMH regulations) regarding assessment of capacity to consent.

Research Procedures: We have described above the potential risks of the research procedures and the safeguards that will be used to minimize risks. These include termination of subjects from research participation if it is believed that such participation endangers their welfare. Monitoring procedures are used to evaluate potential side effects of research procedures. The protocol stipulates an extensive medical, neurological, and psychiatric evaluation of all subjects as a condition for research participation.

Methods to Protect Confidentiality

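### The numeric renal rule acts only on the Week 12 draw; the Week 26 creatinine and eGFR have no stated threshold or action, with 26 weeks of dosing left

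*Protocol*

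**What the plan says.** The rule is reason 3 under Criteria for Early Discontinuation. It begins "Based on the result of a blood draw at the week 12 visit" and acts "if the serum creatinine level increases to be greater than 1.5 mg/dl, or eGFR declines to less than 44 mL/min". The dose then falls to 2 g a day of drug or placebo, labs are repeated at an extra visit at Week 16, and study medication stops if kidney function is still outside the limits.

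The lab schedule is wider than the rule. Under Blood and other Biological Samples, the routine laboratory paragraph says "At Screening, Weeks 12, 26 and 52, blood will be collected for the following screening laboratory tests", and its panel names creatinine and eGFR. The 26-Week Visit section agrees: "Blood will be drawn for the following laboratory analyses: SMAC Blood Chemistry and Complete Blood Count". Neither place says what is done with an abnormal renal result at Week 26.

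The protocol does give general authority to act. Reason 1 states "All medically relevant decisions are made only by study physicians and the PI". The Baseline/Week 0 Visit section states "Dosing is monitored by the Study Physician". The Research Procedures paragraph on minimizing risks provides for "termination of subjects from research participation if it is believed that such participation endangers their welfare".

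Two further statements bear on why renal function matters. Exclusion 8 defines renal failure at entry as an eGFR below 44. The Common Side Effects paragraph says that hallucinations, delirium and seizures at 2 to 4 g a day affect fewer than 1% of patients, all of them with renal failure.

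**The concern.** The protocol decided that, at Week 12, an eGFR below 44 is serious enough to remove dosing from individual judgement. It gives no reason for treating the same value differently at Week 26, although half of the dosing period is still to come and the result is already being collected.

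Elsewhere the protocol writes triggers that hold throughout. A C-SSRS score of 4 or more leads to review whenever it occurs, and an MMSE below 18 at any point leads to a capacity assessment. The restriction to Week 12 therefore looks more like an omission than a decision.

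What is at stake is participant safety. Participants may be up to 95 years old, and the 4 g target is above the 3 g that the protocol gives as the top of the approved range for peripheral HSV infection. A patient whose eGFR first falls below the limit between Weeks 12 and 26 meets the protocol's own entry definition of renal failure, and no dose change is prescribed.

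**Working it through.** **1. Rule against schedule**

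| Renal lab | On study drug? | Numeric action in visible text |
|---|---|---|
| Screening | No | eGFR below 44 excludes |
| Week 12 | Yes | Cut to 2 g, recheck |
| Week 16 (only if flagged at Week 12) | Yes | Stop if still abnormal |
| Week 26 | Yes | None |
| Week 52 | Dosing ends | None needed |

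Week 26 is the only scheduled on-drug draw before the end of dosing that has no rule.

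**2. Time involved**

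- Dosing left after the Week 26 draw: 52 − 26 = 26 weeks.
- Time with no numeric renal rule: 52 − 12 = 40 weeks for a patient normal at Week 12, or 52 − 16 = 36 weeks for one rechecked at Week 16 and kept on drug.

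**3. Planned dose involved**

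The titration is 2 g from Baseline, 3 g from Week 2 and 4 g from Week 4.

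- To Week 12: 2 × 14 + 3 × 14 + 4 × 56 = 28 + 42 + 224 = 294 g.
- Weeks 12 to 52: 40 × 7 × 4 = 1,120 g. Total: 294 + 1,120 = 1,414 g.
- Weeks 26 to 52 at 4 g: 26 × 7 × 4 = 728 g, and 728/1,414 = 51%.
- If the rule applied at Week 26 and the patient was still abnormal four weeks later: 4 × 7 × 2 = 56 g, then stop.
- If the patient recovered and stayed at 2 g: 26 × 7 × 2 = 364 g. Reason 3 does not say whether the dose goes back up after recovery, so staying at 2 g is an assumption.

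These figures describe planned dose when nobody intervenes. They do not measure harm.

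**4. Patients who could still be reached**

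The inputs are in Summary of Experiences to Date: 56 planned, 24 completed, 3 withdrew consent, 1 was withdrawn, and 49 agreed to be randomized.

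- Upper figure: 56 − 24 − 3 − 1 = 28, taking the four early exits as separate from the 24. About 28/2 = 14 are on drug if the arms are even.
- Lower figure: 56 − 49 = 7 still to be randomized. It is 7 + 4 = 11 if the four patients held up by the research pause are among the 49.

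**5. Expected events**

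Taking the protocol's rate at face value, 14 × 0.01 = 0.14, so fewer than 0.14 severe CNS events among those on drug. At the lower figure, 7/2 = 3.5 on drug and 3.5 × 0.01 = 0.035, so fewer than 0.04. The documents give no rate of eGFR decline, so the number of patients who would be flagged cannot be estimated.

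**The case against.** The strongest reply is that the patient is not unprotected. Physicians monitor dosing, 2 g a day is permitted, interruption of up to six weeks is allowed, and participation can be ended if it endangers the patient. That stands. A reader might infer that a patient with an eGFR of 40 at Week 26 must stay on 4 g. The documents do not say so. What is missing is a defined trigger, and the response may differ between physicians.

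The link to harm is also partly inferred. The side-effect paragraph speaks of renal failure without giving an eGFR. The value of 44 comes from the entry criterion and from reason 3, and nothing states that CNS events begin there.

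Two stronger readings should be set aside:

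- A reader might conclude that dosing starts without a renal check because the Baseline blood list has no chemistry panel. In fact creatinine and eGFR are measured at Screening, typically one week earlier, and eGFR is applied as an exclusion. The most that can be said is that no renal lab is scheduled between Screening and Week 12, so both telephone dose increases occur without an on-drug value. A further Baseline assay would not change that.
- A reader might cite the heart-rate rule as one that covers the whole trial. It acts on an EKG that is limited to patients aged 60 or older and repeated only if the initial EKG is abnormal, so it does not support the comparison.

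Finally, part of Study Procedures is not in the available text, and exclusion 8 refers to a section 4.3.b. that cannot be seen. Either could hold a wider renal rule.

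**Conclusion.** The gap is real on the visible text, and it is narrow. A numeric rule that the protocol considered necessary at Week 12 does not extend to the one later on-drug renal result that could still change dosing. For a patient who first crosses the limit at Week 26, the response over the remaining 26 weeks depends on the individual physician.

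The gain in expected events is small, fewer than 0.14 on the protocol's own rate, so the recommendation rests on how little it costs. It is a modest improvement that should be made. It does not show that the trial is unsafe.

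The conclusion assumes that no further renal rule exists in the text that is not available. If one does, reason 3 should cross-refer to it, because its present wording confines the action to Week 12. The counts assume even allocation and that the four early exits are separate from the 24 completers.

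**What to change.** Reword reason 3 so that it applies to any creatinine or eGFR result obtained on study drug, including Week 26 and unscheduled draws. The limits stay as they are. A result outside them leads to a cut to 2 g a day of drug or placebo, a recheck four weeks later (Week 30 after a Week 26 result), and a stop if it is still abnormal.

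No new scheduled draw is needed. A flagged patient has one extra recheck visit and takes a lower dose for at least four weeks. Some patients, in either arm, may stop study drug, which is a real cost in a pilot with 28 patients per arm. They would still be followed to Week 52 where feasible and analysed as randomized, as the protocol already provides for early discontinuation. The rule acts on lab values without reference to treatment, so the blind is kept.

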Valacyclovir, a pro-drug of acyclovir, is the most widely used generic antiviral drug with over 15 years of worldwide use. It is approved for the treatment of HSV1, HSV2, varicella zoster (shingles), and chickenpox. No other available antiviral drug, e.g., acyclovir (intravenous), famciclovir and ganciclovir, has been shown to be superior to valacyclovir in the treatment of HSV1 and HSV2.

Recommended dose of oral valacyclovir for peripheral acute HSV infections is 1 to 3 g daily, and bioavailability is 54%. For long-term HSV suppression, the dose is 1 g daily. In patients with HIV infection and clinical AIDS, valacyclovir 8 g/day was associated with serious adverse events in 10% of patients including GI disturbances and headache, and thrombotic microangiopathy in a few cases. The difficulty in obtaining efficacy for any drug in AD or MCI has led us to target a dose of valacyclovir 4 g daily; 3 g is the upper end of approved doses for peripheral HSV infection and was effective in the schizophrenia pilot trial. Doses of 6-8 g daily are tolerated in healthy young adults but are toxic in patients with HIV. These high doses increase the risk of CNS toxicity including hallucinations and tremor, particularly in older adults with renal insufficiency. Therefore, for older adults with amnesic MCI, we have chosen the dose range of 4 g daily (valacyclovir will begin at 2 g daily (1 g twice daily) and then increase by 1 g/d every 2 weeks until 4 g/d (2 g twice daily) or the maximum tolerated dose that is then kept constant) this provides an acceptable tradeoff between the likelihood of therapeutic efficacy and risk of toxicity.

Based on our experience to date in the conduct of NYSPI protocol #7537; HSV1/HSV2 seropositivity rate is estimated to be 60-65%. Of the 76 patients we anticipate screening in one year's duration, we anticipate 52 patients to be HSV seropositive and recruiting 50 of these 52 eligible patients. Valacyclovir does not have any major drug-drug/drug-food interactions. The proposed

trial is appealing because it involves a novel, unique, understandable mechanism, uses oral capsules rather than I.V. medications, and valacyclovir is very safe.

Significance and Innovation: Antiviral treatment in AD-biomarker positive amnesic MCI (eMCI or IMCI) has not yet been studied in a clinical trial. This is the first clinical trial investigating the use of antiviral treatment in MCI.

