cholinesterase inhibitors and/or memantine throughout the duration of the study. Any changes to the medication will be documented in the participant research chart. Medications given for other medical reasons, e.g., antidiabetic or anti-hypertensive medications, will not be altered for the purposes of this trial and the patient's primary physician may adjust such medications as medically indicated throughout the trial. Psychotropic and other medications are allowed. Details of concomitant medication use will be documented at all visits and will be available for statistical analysis.	
7. Either PET amyloid scan positivity or prior CSF biomarker positive for AD (A β 42 and tau/p- tau).	Medical Records or through completing a PET Scan as part of screen
8. A family member, friend, or other individual who is in contact with the patient agrees to serve as the patient's informant during the study and signs the "Informant Information Sheet."	Patient Designation
Exclusion:	
1. Current clinical diagnosis of schizophrenia, schizoaffective disorder, other psychosis, bipolar disorder or current major depression by DSM-5 criteria. Prior history of major depression will not be exclusionary (25% of older adults have a lifetime history of major depression).	Physician Evaluation
2. Active suicidal intent or plan.	Physician Evaluation with SRMP Assessment
3. Current or recent (past 6 months) alcohol or substance use disorder (DSM-5 criteria).	Physician Evaluation
4. Current diagnosis of other major neurological disorders, including Parkinson's disease, multiple sclerosis, CNS infection, Huntington's disease, and amyotrophic lateral sclerosis.	Physician Evaluation
5. Clinical stroke with residual clinical deficits. MRI findings of cerebrovascular disease (small infarcts, lacunes, periventricular disease) in the absence of clinical stroke with residual neurological deficits will not lead to exclusion.	Physician Evaluation
6. Acute, severe, unstable medical illness. For cancer,	Physician Evaluation

patients with active illness or metastases in the last 12 months will be excluded, but past history of successfully treated cancer will not lead to exclusion.	
7. Sitting blood pressure > 160/100 mm Hg.	Physician Evaluation
8. Renal failure as determined by an estimated Glomerular Filtration Rate (GFR) < 44 ml/min/1.73m ² (see 4.3.b.).	Laboratory Report
9. Serum vitamin B12 levels below the normal range.	Laboratory Report

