Patients who experience any of these changes will be permitted to continue study participation.

Psychotropic and other medications will be permitted. Medication dosage of psychotropics may be changed during the trial if indicated by the patient's physician. All medication changes will be documented in the patient's study chart.

Common Side Effects: headache 14% drug versus 10% placebo, dizziness 2% drug versus 1% placebo in the largest placebo-controlled trial (n=609). Hallucinations, delirium and seizures occur in less than 1% of patients taking 2-4 g daily, and only in patients with renal failure. Valacyclovir at a high dose of 8 g daily in HIV led to SAEs in 10% of patients. Valacyclovir 3 g daily was efficacious in a randomized, double-blind, placebo-controlled, 18-week trial in 24 patients with schizophrenia with positive HSV1 titers, valacyclovir 3 g/day was superior to placebo with effect sizes of 0.79, 0.97 and 1.14 for tests of working memory, verbal memory, and visual object memory, respectively, from the computerized Penn battery (Prasad et al. 2013). Given the difficulty with achieving efficacy in MCI, we chose 4 g daily to ensure that we do not underdose while avoiding known toxicity associated with much higher doses. In our ongoing VALAD trial that targets a dose of 4 g daily, 2 of 76 patients have discontinued because of putative side effects (double-blind maintained, so they may be on drug or placebo), and 3 of 76 patients have continued at a lower dose of 2 or 3 g valacyclovir/placebo daily (2 g or higher is permitted). It is not uncommon for medical illness to lead to interruption of treatment, usually for short intervals (e.g., surgery). During the study, interruption of treatment with a visit delay for up to 6 weeks will be permitted. Treatment and data collection will resume after the interruption and the patient will continue in the protocol. All serious adverse events will be reported to our IRB and the DSMB.

Neuropsychological Assessment: During neuropsychological testing, some subjects may find some questions upsetting. The tester will discuss the situation with the patient and will allow for an expanded break between tests when feasible. If the patient still chooses not to proceed with testing, the patient's choice will be respected.

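### Renal rule and toxicity statement do not fit together: a patient below the eGFR the protocol calls renal failure stays on 2 g/day until Week 16

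*Protocol*

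**What the plan says.** Three places in the Protocol bear on renal function and study drug.

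- **Inclusion/Exclusion Criteria, exclusion 8** bars patients with "Renal failure as determined by an estimated Glomerular Filtration Rate (GFR) < 44" (unit there: ml/min/1.73m²). This is the only definition of renal failure in the available text.
- **Risks/Discomforts/Inconveniences, Common Side Effects** states: "Hallucinations, delirium and seizures occur in less than 1% of patients taking 2-4 g daily, and only in patients with renal failure".
- **Criteria for Early Discontinuation, item 3** applies to the Week 12 blood draw. Its trigger is "if the serum creatinine level increases to be greater than 1.5 mg/dl, or eGFR declines to less than 44 mL/min". The action is "we will lower the study medication to the minimum dose of 2 g valacyclovir or placebo per day", followed by repeat tests at an added Week 16 visit. Then: "If, at week 16, kidney function is still abnormal based on the above criteria, study medication will be discontinued for this patient". The primary care physician is told.

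Two dosing statements in the Baseline/Week 0 Visit section also matter. "The maintenance dose of valacyclovir is 4g daily per protocol", and a patient who cannot tolerate that dose may remain on active treatment provided the daily dose is at least 2 g.

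**The concern.** Taken at face value, the three statements conflict. The eGFR level that bars a patient from entry is the level at which item 3 keeps a patient on treatment. The dose it keeps them on lies inside the range in which the protocol says the serious neuropsychiatric events occur, and this is the only group in which it says they occur.

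What is at stake is participant safety, and whether the written rule gives study physicians, the DSMB and the IRB a consistent account of who is at risk. The trial enrols patients aged 50 to 95, and the Background section itself singles out older adults with renal insufficiency when it discusses CNS toxicity.

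**Working it through.** The plan gives no figure to reproduce on this point. The check sets the passages side by side, with simple arithmetic.

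1. **Threshold.** Exclusion 8: eGFR < 44. Item 3: eGFR < 44. The number is the same. The units are written differently (ml/min/1.73m² against mL/min); I assume one eGFR scale is meant.

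2. **Dose range.** The side-effect statement covers 2 to 4 g daily. Item 3's reduced dose is 2 g daily, the lower bound of that range and so inside it.

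3. **Length of exposure.** Week 12 to Week 16 is (16 − 12) × 7 = 28 days. At 2 g/day that is 28 × 2 = 56 g for a patient on active drug. This is nominal: it treats the reduction as taking effect on the day of the Week 12 visit.

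4. **Size of the dose step.** The protocol permits 2, 3 or 4 g daily, so the proportional reduction under item 3 is:
   - from 4 g: 1 − 2/4 = 50%
   - from 3 g: 1 − 2/3 = 33%
   - from 2 g: 1 − 2/2 = 0%

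   A patient already at 2 g for intolerance therefore gets no dose action before Week 16.

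5. **Gradation.** Item 3 has one step for every value below 44. An eGFR just under 44 and a much lower one get the same written action.

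6. **Creatinine trigger.** A patient who meets only the creatinine limit may have an eGFR of 44 or more and so fall outside exclusion 8. The conflict concerns the eGFR trigger.

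7. **Who could still meet the rule.** The Summary of Experiences to Date reports 49 who agreed to randomization, 24 completed, 3 who withdrew consent and 1 withdrawn by the study. Taking the last three counts as part of the 49, 49 − 24 − 3 − 1 = 21 were unfinished. With 56 planned, 56 − 49 = 7 were still to enter. That gives at most 21 + 7 = 28 across both arms, fewer once those already past Week 12 are removed. It is a ceiling on patients to whom item 3 could apply, not an estimate of those who would cross 44. The protocol gives no such estimate.

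**The case against.** The strongest reply is that this is a tension rather than a proven contradiction.

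- **Meaning of renal failure.** The side-effect sentence summarises background experience and does not say how renal failure was defined there. It may mean something more severe than eGFR below 44, and item 3 does not use the term. This stands as a possibility. But exclusion 8 attaches the term to 44, and nothing tells the reader that the side-effect text means something else.

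- **Dose-related risk.** The Background section describes CNS toxicity in renal insufficiency in connection with doses of 6 to 8 g. On that reasoning a lower dose is a coherent response. This also stands, and it means item 3 is not arbitrary. It does not square with a separate sentence that places the events at 2 to 4 g, and it does not help the patient whose dose is already 2 g.

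- **Entry and follow-up are different decisions.** Refusing a patient at screening is not the same as responding to one new abnormal result, and item 3 is graduated: reduce, repeat, then stop. That is a fair defence of having different rules. The protocol does not offer it as the reason, and it leaves the side-effect statement unanswered.

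- **Discretion.** The study physician monitors dosing (Baseline/Week 0 Visit). Treatment may be interrupted for up to 6 weeks for intervening conditions (Treatment Interruption). The principal investigator may discontinue for severe illness (Criteria for Early Discontinuation, item 1), and participation can be ended on welfare grounds (Research Procedures, under minimizing risks). These are real safeguards, and item 3 is not the only route off treatment. None is tied to the eGFR trigger, for which the written instruction is to continue.

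- **Text not available.** Exclusion 8 refers to a section 4.3.b that is not in the available text, and part of Study Procedures is not available either. A further renal provision or an extra contact between Weeks 12 and 16 could be there.

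**Conclusion.** The renal inconsistency stands. Exclusion 8, the side-effect statement and item 3 cannot all be read literally. As written, a patient whose eGFR falls below 44 stays for a nominal 28 days on a dose inside the range the protocol links to neurotoxicity in renal failure. This assumes that renal failure means the same thing in both places and that the two eGFR limits share a scale. The point merits correction because it concerns safety and is cheap to settle. It does not show that any patient has been harmed or that the dose rule is clinically wrong.

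Three stronger readings are tempting, and the documents do not support them.

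- **HIV.** A reader might infer a second contradiction because HIV is named as a setting of toxicity but not as an exclusion. The statements concern higher doses: "Doses of 6-8 g daily are tolerated in healthy young adults but are toxic in patients with HIV" and "Valacyclovir at a high dose of 8 g daily in HIV led to SAEs in 10% of patients". Against the 4 g target these are 6/4 = 1.5 and 8/4 = 2 times the dose. No HIV toxicity is reported at 2 to 4 g, and the protocol already explains 4 g as avoiding toxicity seen at much higher doses.

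- **Distorted cognitive outcomes.** A reader might infer that delirium in this interval would corrupt the PACC. The PACC is given at Baseline and Weeks 12, 26 and 52, so no scheduled assessment falls between Weeks 12 and 16.

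- **A high event rate below 44.** A reader might infer that a rate under 1% overall, confined to renal failure, implies a known larger rate in these patients. The documents give neither the share of that background population with renal failure nor its definition, so no rate can be derived.

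**What to change.** The investigators, with the DSMB and IRB, should reconcile exclusion 8, the Common Side Effects statement and item 3. Either of two routes would do it:

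1. Make item 3 consistent with the toxicity statement for patients who meet the protocol's own definition of renal failure. The text should cover the period between the Week 12 result and Week 16, and patients already at 2 g/day.
2. Have the Common Side Effects text say what it means by renal failure and why the statement does not apply at this eGFR.

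Either route should also say how patients who meet only the creatinine limit are treated in relation to exclusion 8. No dose or stopping rule is proposed here; the clinical decision belongs to those bodies.

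The cost is a wording amendment. If the chosen route changes treatment for any patient, that patient remains in intention-to-treat follow-up to Week 52 where feasible, as the protocol already provides, so the analysis set is unaffected.
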